### COVID-19 Pandemic-Related Acceptable Protocol Modification

During the COVID 19 pandemic, it has been necessary to employ mitigation strategies to enable the investigator to ensure subject safety and continuity of care. Acceptable mitigation strategies are identified and included in the Operations Manual in [Appendix F](#).

The investigator should contact the sponsor medical contact before discontinuing a subject from the study for a reason other than described in the protocol, to ensure all acceptable mitigation steps have been explored.

Refer to the Operations Manual in [Appendix F](#) for details on how to handle study activities/procedures.

### Interruption/Discontinuation of Study Drug Due to COVID-19 Infection

During the study drug dosing period, a subject with confirmed (viral test positive) or suspected COVID-19 infection can only be dosed with study drug if the following COVID-19 viral clearance criteria are met:

- At least 14 days since first positive test result have passed in asymptomatic patients or at least 14 days since recovery, defined as resolution of fever without use of antipyretics and improvement in symptoms.

Delays in study drug dosing due to the above COVID-19 testing guidance for subjects must be discussed with the AbbVie medical contact, along with the possibility of premature discontinuation from the study drug dosing period. Follow subsequent protocol Section 5.6 for subjects who discontinued study drug.

## 5.6 Follow-Up After Subject Discontinuation of Study Drug or from Study

---

To minimize missing data for efficacy and safety assessments, subjects who prematurely discontinue study drug treatment should continue to be followed for all regularly scheduled visits, unless subjects have decided to discontinue the study participation entirely (withdrawal of informed consent). Subjects should be advised on the continued scientific importance of their data even if they discontinue treatment with study drug early.

If, during the course of study drug administration, the subject prematurely discontinues study drug use, the subject has the option to continue in the study and complete the remaining visits as scheduled. If remaining visits will be completed, a PD visit is not required. If the subject does not continue in the study, the procedures outlined for the PD visit must be completed, ideally within 2 weeks of the decision and preferably prior to the initiation of another therapy. However, these procedures should not interfere with the initiation of any new treatments or therapeutic modalities that the Investigator feels are necessary to treat the subject's condition.

Following discontinuation of the study drug, the subject will be treated in accordance with the Investigator's best clinical judgment.

If a subject prematurely discontinues study participation (withdrawal of informed consent), the procedures outlined for the Premature Discontinuation visit (PD visit) should be completed as soon as possible, preferably within 2 weeks. In addition, if subject is willing, a follow-up phone call approximately 140 days (20 weeks) after the last dose of risankizumab or approximately 28 days after the last dose of apremilast may be completed to ensure all treatment-emergent AEs/serious adverse events (SAEs) have been resolved. The 140-day (20-week) or 28-day follow-up phone calls following the last dose of risankizumab or apremilast, respectively, during the trial will not be required for any subject

who initiates commercially available risankizumab or apremilast upon or after the study Completion Visit (i.e., Week 52 or during the follow-up period) or PD visit.

If a subject withdraws from study follow up or withdraws permission for the collection of their personal data, the study staff may still use available public records to obtain information about survival status only, as appropriate per local regulations.

## 5.7 Study Drug

Study site staff will administer risankizumab (150 mg [1 × 1 mL 150 mg/mL pre-filled syringe]) subcutaneously or study staff will provide apremilast (30 mg [10 mg, 20 mg, 30 mg, film-coated tablets]) beginning at Baseline (Day 1) (Table 2).

Apremilast subject dosing (orally) will be recorded on a subject dosing diary. The subject will be instructed to return all apremilast packaging (even if empty) to the study site personnel at each study visit. The study site personnel will document compliance.

**Table 2. Identity of Investigational Product**

| Study Drug              | Dosage Form  | Strength                                | Route of Administration | Manufacturer |
|-------------------------|--|---|-------------------------|--------------|
| Risankizumab (ABBV-066) | Solution for injection in pre-filled syringe (PFS) | 150 mg (1x 1 mL 150 mg/mL PFS)          | Subcutaneous injection  | AbbVie       |
| Apremilast              | Tablets  | 10 mg, 20 mg, 30 mg film-coated tablets | Oral                    | Amgen        |

AbbVie will not supply drug other than risankizumab and apremilast. AbbVie provided study drugs should not be substituted or alternately sourced unless otherwise directed by AbbVie.

Open-label risankizumab and apremilast will be packaged in quantities sufficient to accommodate study design. Each risankizumab kit or apremilast package will be labeled per local requirements and this label must remain affixed to the respective packaging. Upon receipt, study drug should be stored as specified on the label in their original packaging and kept in a secure location. A temperature log must be maintained for documentation. Each kit or package will contain a unique kit or package number. This number is assigned to a subject via interactive response technology (IRT) and encodes the appropriate study drug to be dispensed at the subject's corresponding study visit. All blank spaces on the label will be completed by the site staff prior to dispensing to subjects. Study drugs will only be used for the conduct of this study.

## 5.8 Randomization/Drug Assignment

All subjects will be assigned a unique identification number by the IRT at the screening visit. For subjects who rescreen, the screening number assigned by the IRT at the initial screening visit should be used. The IRT will assign a randomization number that will encode the subject's treatment group assignment according to the randomization schedule.

Study treatment duration includes Period A and Period B:

- Period A (Baseline to Week 16): Eligible subjects will be centrally randomized at the Baseline (Day 1) visit in a 1:2 ratio to receive either risankizumab 150 mg as a single SC injection (Arm 1) or apremilast orally with a dose titration from Day 1 to Day 5 and continuing with 30 mg BID until the day prior to Week 16 (Arm 2). The randomization will be stratified by Baseline body weight ( $\leq 100$  kg,  $> 100$  kg) and prior exposure to any systemic and/or biologic treatment for PsO (0,  $\geq 1$ ).
- Period B (Week 16 to Week 52): Subjects initially randomized to apremilast (Arm 2) will be rerandomized at the Week 16 visit in a 1:1 ratio to receive either risankizumab 150 mg as a single SC injection (Arm 2a) or apremilast 30 mg orally BID (Arm 2b). Rerandomization will be stratified by PASI 75 response (responder, non-responder) at Week 16. Rescue risankizumab will be offered for subjects who are re-randomized to the apremilast arm and are PASI 50 non-responders at Week 28 (Arm 3a) or Week 40 (Arm 3b).

This is an open-label study; however, the efficacy assessor will remain blinded to each subject's treatment, clinical laboratory results, and all subject safety data during the course of the study.

In the event of a medical emergency in which the Investigator believes that knowledge of study drug treatment is required for the efficacy assessor, reasonable efforts must be made to contact the AbbVie Emergency Contact.

The date and reason that the efficacy assessor's blind was broken must be recorded in the source documentation and eCRF, as applicable.

## 5.9 Protocol Deviations

---

AbbVie does not allow intentional/prospective deviations from the protocol except when necessary to eliminate an immediate hazard to study subjects. The investigator is responsible for complying with all protocol requirements, written instructions, and applicable laws regarding protocol deviations. If a protocol deviation occurs (or is identified, including those that may be due to the COVID-19 pandemic), the investigator is responsible for notifying IEC/IRB, regulatory authorities (as applicable), and AbbVie.

## 6 SAFETY CONSIDERATIONS

### 6.1 Complaints and Adverse Events

---

#### Complaints

A complaint is any written, electronic, or oral communication that alleges deficiencies related to the physical characteristics, identity, quality, purity, potency, durability, reliability, safety, effectiveness, or performance of a product/device. Complaints associated with any component of the investigational products must be reported to AbbVie.

## Product Complaint

A product complaint is any complaint related to the biologic or drug component of the product or to the medical device component(s).

For a product this may include, but is not limited to, damaged/broken product or packaging, product appearance whose color/markings do not match the labeling, labeling discrepancies/inadequacies in the labeling/instructions (e.g., printing illegible), missing components/product, device damage or not working properly, or packaging issues.

Product complaints concerning the investigational products and/or device must be reported to AbbVie within 24 hours of the study site's knowledge of the event.

Reporting will be done via electronic data capture (EDC). The date the product complaint details are entered into EDC and the form is saved represents the date reported to AbbVie. A back-up paper form will be provided for reporting complaints related to unassigned product or in the event of an EDC system issue. If a back-up paper form is used, the date the form is emailed to RD\_PQC\[contact] represents the date reported to AbbVie.

All follow-up information is to be reported to the sponsor (or an authorized representative) and documented in source as required by the sponsor. Product complaints associated with adverse events will be reported in the study summary. Product complaints occurring during the study will be followed up to a satisfactory conclusion.

## Medical Complaints/Adverse Events and Serious Adverse Events: Study Drug

An AE is defined as any untoward medical occurrence in a subject or clinical investigation subject administered a pharmaceutical product and which does not necessarily have a causal relationship with this treatment. An AE can therefore be any unfavorable and unintended sign (including an abnormal laboratory finding), symptom, or disease temporally associated with the use of a medicinal (investigational) product, whether or not the event is considered causally related to the use of the product.

Such an event can result from use of the drug as stipulated in the protocol or labeling, as well as from "special situations" such as accidental or intentional overdose, medication error, occupational or accidental exposure, off-label use, drug abuse, drug misuse, or drug withdrawal, all which must be reported whether associated with an AE or not. Any worsening of a pre-existing condition or illness is considered an AE. Worsening in severity of a reported AE should be reported as a new AE. Laboratory abnormalities and changes in vital signs are considered to be AEs only if they result in discontinuation from the study, necessitate therapeutic medical intervention, and/or if the investigator considers them to be AEs.

The investigators will monitor each subject for clinical and laboratory evidence of AEs on a routine basis throughout the study. All AEs will be followed to a satisfactory conclusion.

An elective surgery/procedure scheduled to occur during a study will not be considered an AE if the surgery/procedure is being performed for a pre-existing condition and/or the surgery/procedure has been pre-planned prior to study entry. However, if the pre-existing condition deteriorates unexpectedly

during the study (e.g., surgery performed earlier than planned), then the deterioration of the condition for which the elective surgery/procedure is being done will be considered an AE.

If an AE, whether associated with study drug or not, meets any of the following criteria, it is to be reported to AbbVie clinical pharmacovigilance as an SAE within 24 hours of the site being made aware of the SAE (refer to Section 4.3 of the Operations Manual for reporting details and contact information):

|  |   |
|--|---|
| Death of Subject  | An event that results in the death of a subject.  |
| Life-Threatening  | An event that, in the opinion of the investigator, would have resulted in immediate fatality if medical intervention had not been taken. This does not include an event that would have been fatal if it had occurred in a more severe form.  |
| Hospitalization or Prolongation of Hospitalization  | An event that results in an admission to the hospital for any length of time or prolongs the subject's hospital stay. This does not include an emergency room visit or admission to an outpatient facility.   |
| Congenital Anomaly  | An anomaly detected at or after birth, or any anomaly that results in fetal loss.   |
| Persistent or Significant Disability/Incapacity   | An event that results in a condition that substantially interferes with the activities of daily living of a study subject. Disability is not intended to include experiences of relatively minor medical significance such as headache, nausea, vomiting, diarrhea, influenza, and accidental trauma (e.g., sprained ankle).  |
| Important Medical Event Requiring Medical or Surgical Intervention to Prevent Serious Outcome | An important medical event that may not be immediately life-threatening or result in death or hospitalization, but based on medical judgment may jeopardize the subject and may require medical or surgical intervention to prevent any of the outcomes listed above (i.e., death of subject, life-threatening, hospitalization, prolongation of hospitalization, congenital anomaly, or persistent or significant disability/incapacity). Additionally, any elective or spontaneous abortion or stillbirth is considered an important medical event along with any suspected transmission of an infectious agent via a medicinal product if no other serious criterion is applicable. Examples of such events include allergic bronchospasm requiring intensive treatment in an emergency room or at home, blood dyscrasias or convulsions that do not result in inpatient hospitalization, or the development of drug dependency or drug abuse. |

All AEs reported from the time of risankizumab or apremilast administration until 140 days (20 weeks) after discontinuation of risankizumab administration or 28 days after discontinuation of apremilast administration will be collected, whether solicited or spontaneously reported by the subject. After 140 days (20 weeks) following the last dose of study drug or completion of study treatment only

spontaneously reported SAEs will be collected (nonserious AEs will not be collected.) In addition, study procedure-related serious and nonserious AEs will be collected from the time the subject signs the study-specific informed consent. If a subject prematurely discontinues study participation and begins commercially available risankizumab (Skyrizi) or apremilast (Otezla) all adverse events reported by healthcare professionals or the patient, will be captured as postmarketing reports. The follow-up phone call following the last dose of risankizumab during the study will not occur for subjects who begin commercially available risankizumab or apremilast.

The following definitions will be used for Serious Adverse Reactions (SAR) and Suspected Unexpected Serious Adverse Reaction (SUSAR):

- |              |   |
|--------------|---|
| SAR   | Defined as all noxious and unintended responses to an Investigational Medicinal Product (IMP) related to any dose administered that result in an SAE as defined above.  |
| SUSAR | Refers to individual SAE case reports from clinical trials where a causal relationship between the SAE and the IMP was suspected by either the sponsor or the investigator, is unexpected (not listed in the applicable Reference Safety Information [RSI]), and meets one of the above serious criteria. |

AbbVie will be responsible for SUSAR reporting for the IMP in accordance with global and local requirements.

Adverse events will be monitored throughout the study to identify any of special interest that may indicate a trend or risk to subjects.

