## 4 INVESTIGATIONAL PLAN

### 4.1 Overall Study Design and Plan

---

This is a Phase 4, global, multicenter, randomized, open-label, efficacy assessor-blinded, active comparator study examining the effect of risankizumab compared to apremilast in adult subjects with moderate plaque PsO who are candidates for systemic therapy.

The study is designed to enroll 330 subjects. See Section 5.1 for information regarding enrollment criteria.

The study duration for subjects administered risankizumab or provided apremilast will be up to approximately 69 weeks or 61 weeks, respectively. The study is comprised of a Screening period of up to 35 days, a 52week treatment period, and a follow-up phone call for safety. Depending on the

[figure not shown]
treatment at the end of the study, the follow-up phone call for safety will be conducted approximately 20 weeks (140 days) after administration of the last dose of risankizumab (i.e., Week 40 for subjects originally randomized to risankizumab and Week 44 for subjects switched from apremilast to risankizumab) or approximately 4 weeks (28 days) after the last dose of apremilast (for subjects who remain on the APR arm after re-randomization).

The 52-week treatment duration includes Period A and Period B:

- Period A (Baseline to Week 16): Eligible subjects will be centrally randomized at the Baseline (Day 1) visit in a 1:2 ratio to receive either risankizumab 150 mg as a single subcutaneous (SC) injection (Arm 1) or apremilast 30 mg orally twice daily (BID) (Arm 2). The randomization will be stratified by Baseline body weight ( $\leq 100$  kg,  $> 100$  kg) and prior exposure to any systemic and/or biologic treatment for PsO (0,  $\geq 1$ ). Study drug administration for apremilast will occur beginning at Baseline (Day 1) based on the dose titration schedule from Day 1 to Day 5 and will continue with 30 mg BID until the day prior to the Week 16 visit where re-randomization will occur. Study drug administration for risankizumab will occur at Baseline (Day 1) and Week 4. The final efficacy evaluation for Period A will take place at Week 16.

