10.2.1 Treatment-Emergent Adverse Events

A treatment-emergent adverse event (TEAE) in each analysis period is defined as follows:

A TEAE in Period A is defined as any AE with an onset date on or after the first dose of study drug in Period A, and

- Within the minimum of (i) 140 days after the last dose of RZB in Period A and (ii) the first dose date of study drug in Period B for subjects who receive RZB at Baseline.
- Within the minimum of (i) 28 days after the last dose of APR in Period A and (ii) the first dose date of study drug in Period B for subjects who receive APR at Baseline.

A TEAE in Period B is defined as any AE with an onset date on or after the first dose of study drug in Period B and

- Within 140 days after the last dose of RZB in Period B for subjects who receive RZB in Period B.
- Within the minimum of (i) 28 days after the last dose of APR in Period B and (ii) the first dose date of rescue risankizumab (if any) for subjects who receive APR in Period B.

A TEAE during the administration of rescue risankizumab is defined as any AE with an onset date on or after the first dose of rescue risankizumab and within 140 days after the last dose of rescue risankizumab.

A TEAE during the administration of risankizumab (i.e., among the ALL_RZB Population) is defined as any AE with an onset date on or after the first dose of risankizumab and within 140 days after the last dose of risankizumab.

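### The safety call is dropped for subjects who start commercial risankizumab or apremilast, while the windows for collecting and counting adverse events run on past the last scheduled contact

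*Protocol*

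**What the plan says.** Four rules bear on this point.

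- **Collection.** Under Protocol 6.1, adverse events from first dosing onward "until 140 days (20 weeks) after discontinuation of risankizumab administration or 28 days after discontinuation of apremilast administration will be collected, whether solicited or spontaneously".
- **Counting.** SAP 10.2.1 defines a Period B treatment-emergent event for risankizumab as one with onset "Within 140 days after the last dose of RZB in Period B for subjects who receive RZB in Period B". For apremilast the limit is 28 days after the last dose or the first rescue dose, whichever is earlier.
- **Contact.** In the activity schedule (Protocol Appendix D) the safety call is the only adverse-event assessment after the Week 52/premature discontinuation visit. Section 4.1 places the call about 140 days after the last risankizumab dose, or 28 days after the last apremilast dose, and states no exception.
- **Exemption.** Section 5.6 says that neither the 140-day nor the 28-day call is needed for someone "who initiates commercially available risankizumab or apremilast upon or after the study Completion Visit (i.e., Week 52 or during the follow-up period) or PD visit". Section 6.1 is firmer and names only the risankizumab call: "The follow-up phone call following the last dose of risankizumab during the study will not occur for subjects who begin commercially available risankizumab or apremilast".

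Commercial use is foreseen, since 5.3 permits either product once the Week 52/premature discontinuation assessments are done. For subjects who leave the study early and start a commercial product, 6.1 adds that "all adverse events reported by healthcare professionals or the patient, will be captured as postmarketing reports".

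**The concern.** The plan promises ascertainment over a fixed window and then removes the one scheduled contact that serves the end of it. Three features make this more than a formality.

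First, the exemption is wider than worry about attribution would require. It covers a commercial start at any time in the follow-up period, so weeks in which only study drug had been taken are never asked about. It also crosses products: a risankizumab subject who starts commercial apremilast loses the 140-day risankizumab call.

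Second, the tables of numbers and percentages (SAP 10.2.2 and 10.2.3) keep these subjects in the denominator. The unsolicited stretch differs by arm, and the choice of commercial treatment is not random, so any under-ascertainment need not be balanced.

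Third, SAP 10.2.1 closes the counting window at the next treatment in other cases (first Period B dose, first rescue dose) but not at commercial start. If an Arm 2b subject begins commercial risankizumab after Week 52 and reports a reaction within 28 days of the last apremilast tablet, it counts as an apremilast event.

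**Working it through.** **Inputs.** Protocol 4.1 gives the last risankizumab dose as "Week 40 for subjects originally randomized to risankizumab and Week 44 for subjects switched from apremilast to risankizumab". Rescue Arms 3a and 3b also end at Week 44. Appendix D gives Week 40 = Day 281, Week 44 = Day 309 and Week 52 = Day 365, with a visit window of ±3 days. Screening lasts up to 35 days (5 weeks).

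**Reproducing the plan's durations (4.1).** Risankizumab: 5 + 44 + 20 = 69 weeks. Apremilast: 5 + 52 + 4 = 61 weeks. Both match the stated figures, which confirms where the call falls.

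**Days without scheduled contact for on-schedule Week 52 completers.** Uncontacted days = (last dose day + 140) − 365.

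| Group | Last dose | Window ends | Days after Week 52 | Share of 140 | Share with ±3 days on both visits |
|---|---|---|---|---|---|
| Arm 1 | Day 281 | Day 421 | 56 | 40% | 36–44% |
| Arms 2a, 3a, 3b | Day 309 | Day 449 | 84 | 60% | 56–64% |

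For Arm 2b with apremilast to Week 52, the whole 28-day window follows the last visit (28/28 = 100%).

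**Premature discontinuers.** If the discontinuation visit falls g days after the last risankizumab dose, the share is (140 − g)/140. Over an assumed range of g = 0, 14, 28, 56, 84 and 98 days this gives 100%, 90%, 80%, 60%, 40% and 30%.

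**Time an earlier call would recover.** With commercial start on day s, a call held at that start recovers s − 365 days. For example, a start at Week 58 is Day 58 × 7 + 1 = 407, which recovers 42 days on which no commercial drug had been taken. A start at Week 52 recovers none; there the gain is only that counting stops where collection stops. A risankizumab subject who starts commercial apremilast and keeps the 140-day call recovers the full 56 or 84 days.

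**Numerator against denominator in SAP 10.2.4.** Patient-years already stop at the end of study date + 1 day, but neither document defines that date for exempted subjects. If it is Week 52, exposure runs to Day 366 while the counting window runs to last dose + 140.

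| Group | First dose in period | Full window (days) | To Day 366 (days) | Share of window after the cap |
|---|---|---|---|---|
| Arm 1, Period B | Day 113 | 308 | 253 | 18% |
| Arm 2a | Day 113 | 336 | 253 | 25% |
| Arm 3a | Day 197 | 252 | 169 | 33% |
| Arm 3b | Day 281 | 168 | 85 | 49% |

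A spontaneous report in that last stretch would enter the numerator with no matching exposure.

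**The case against.** The strongest reply is that the window is not empty. Section 6.1 takes spontaneous as well as solicited reports, and nothing withdraws that for completers. Any serious event must be reported within 24 hours of the site learning of it. What is lost is scheduled questioning, which matters most for non-serious events. This stands. A reader might infer that 40–60% of the window is uncovered for everyone who starts a commercial product, or that deaths and malignancies go uncounted. The documents do not support either reading: the percentages apply to on-schedule Week 52 completers and describe missing scheduled contact, not missing data.

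A reader might also want a loss in patient-years. That needs commercial uptake, which neither document gives. Moreover, patient-years are already capped at the end of study date, so exposure-adjusted rates are partly protected if that date is Week 52 or the discontinuation visit.

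Nor do the documents say that postmarketing reports stay out of the trial tables; they do not say either way. The Operations Manual, to which Appendix D refers for detail, is not among these documents, so a contact prescribed there cannot be excluded.

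Finally, the consequence is limited. For subjects who enter Period B, Period A counting ends at the first Period B dose, so that comparison is essentially untouched. The safety summaries are descriptive, and the 140-day and 28-day windows differ between drugs by design. All this lowers the weight of the point. It does not reconcile 5.6 and 6.1 with each other or with the collection and counting windows.

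**Conclusion.** The point holds as an inconsistency between contact, collection and counting. For subjects who complete Week 52 on schedule and then start a commercial product, there is no scheduled adverse-event contact for up to 56 of 140 days (40%), 84 of 140 days (60%), or all 28 days, depending on arm. For premature discontinuers the share depends on when the discontinuation visit falls. These figures assume planned dosing and visit dates. The number of subjects affected is unknown.

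The percentage tables can be under-ascertained in Period B and after rescue, and an event after commercial risankizumab can be charged to apremilast. Efficacy is unaffected. Because comparative safety is part of the study objective and the remedy is cheap, the change should be made.

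**What to change.** **Protocol 5.6 and 6.1.** Reconcile the two sections with each other and with the collection window. Replace the exemption with a change of timing: hold the already planned call for every subject at day 140 (risankizumab) or day 28 (apremilast), or at or just before the first commercial dose, whichever is earlier. The exception is a risankizumab subject who starts commercial apremilast, who keeps the 140-day call. After withdrawal of consent the call remains subject to the subject's willingness, as 5.6 already provides.

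**SAP 10.2.1 and 10.2.4.** Add to the minimum that ends each window:

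- the first commercial dose date of either product, for subjects last on apremilast;
- the first commercial risankizumab dose date, for subjects last on risankizumab.

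In 10.2.1 the Period B, rescue and all-risankizumab definitions for risankizumab are now a plain 140 days and would become a minimum. Leave the 140-day window intact for risankizumab subjects who start commercial apremilast, and flag events with onset after that start. A single cut-off at the first dose of any commercial product would discard the events that their retained call is meant to find.

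**End of study date.** Define it for subjects who start a commercial product, so that collection, counting and patient-years end together. State whether postmarketing reports within the window enter the trial tables.

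**Cost.** One planned call is kept rather than cancelled, with protocol wording and one further date in two SAP sections. The downside is that some time after commercial start leaves the treatment-emergent window.
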